12.3 Interim Monitoring Plan

Interim Analysis and Early Stopping Rules

The SRT will review safety data when 3 and 10 subjects treated have had the opportunity to be followed for 30 days, respectively. The study will be stopped if any patients develop grade 4 or higher toxicity attributed to RT rather than to lymphoma progression or other cause as per SRT.

Safety Interim Analysis

The SRT will review AE and SAE information on a regular basis throughout subject treatment in Phase 2 of the study. The SRT may request additional safety data or modifying the study conduct. The sponsor may request additional reviews by the SRT if safety concerns are identified. Data submitted to the SRT may be monitored or unmonitored to facilitate timely review.

Efficacy Interim Analysis

There is no planned efficacy interim analysis for this portion of the study.

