7.4 Procedures for AE and SAE Collection and Reporting

7.4.1 Reporting of Adverse Events

The investigator is responsible for ensuring that all adverse events observed by the investigator or reported by the subject that occur from enrollment (ie, radiation therapy consultation) through 3 months after RT are monitored and reported. After 3 months, targeted adverse events including (eg, neurological, hematological, infections, autoimmune disorders, and secondary malignancies) will be monitored and reported for 6 months after treatment with axicel or tisacel or until disease progression, whichever occurs first.

The investigator must address the below for adverse events:

- Adverse event diagnosis or syndrome (if not known, signs or symptoms)
- Dates of onset and resolution
- Severity
- Assessment of relatedness to investigational product, lymphodepleting chemotherapy or study procedures
- Action taken

In reviewing adverse events, investigators must assess whether the adverse event is possibly related to 1) CAR T cell therapy product 2) RT, or 3) any protocol-required study procedure. The relationship is indicated by a yes or no response and entered into the CRF. A yes response should indicate that there is evidence to suggest a causal relationship between the study treatment or procedure and the adverse event. Additional relevant data with respect to describing the adverse event will be collected in the CRFs.

The investigator is responsible for reviewing laboratory test results and determining whether an abnormal value in an individual study subject represents a clinically significant change from the subject's baseline values. In general, abnormal laboratory findings without clinical significance (based on the Investigator's judgment) are not to be recorded as adverse events. However, abnormal laboratory findings that result in new or worsening clinical sequelae, require therapy or adjustment in current therapy are considered adverse events. Where applicable, clinical sequelae (not the laboratory abnormality) are to be recorded as the adverse event.

The investigator is expected to follow reported adverse events until stabilization or resolution. If a subject begins a new anticancer therapy, the adverse event reporting period for non-serious adverse events ends at the time the new treatment is started.

7.4.2 Reporting of Serious Adverse Events and Non-serious CRS events Grade ≥ 3

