The investigator is responsible for reporting all serious adverse events observed by the investigator or reported by the subject that occur after signing of the consent through 3 months after the RT. After 3 months, only serious targeted adverse events (e.g., neurological, hematological, infections, autoimmune disorders, and secondary malignancies) observed by the investigator or reported by the subject will be reported for 6 months after RT or until disease progression, whichever occurs first. For subjects who screen fail or are enrolled but do not receive RT, the reporting period for serious adverse events ends 30 days after the last procedure (e.g., biopsy).

Serious events that the investigator assesses as related to RT should be reported regardless of the study period.

All serious adverse events and non-serious CRS events \geq Grade 3 ²² must be submitted within 24 hours following the investigators knowledge of the event **using a SAE Report Form. Refer to the SAE Report Form for instructions on how to submit the SAE report.** Subsequently, all serious adverse events will be reported to the health authorities per local reporting guidelines.

Progression of the malignancy during the study should not be reported as a serious adverse event. Adverse events associated with disease progression may be reported as serious adverse event. If the malignancy has a fatal outcome within 3 months of the last day of the lymphodepleting therapy,

CAR T infusion, or RT, then the event leading to death must be recorded as a serious adverse event with CTCAE Grade 5.

Death must be reported if it occurs during the serious adverse event reporting period, irrespective of any intervening treatment.

Any death occurring after the first dose of chemotherapy, for the purpose of pre-lymphodepletion, and within 3 months of the CAR T infusion or RT, regardless of attribution to treatment, requires expedited reporting within 24 hours. Any death occurring greater than 3 months after the CAR T infusion or RT requires expedited reporting within 24 hours only if it is considered related to treatment.

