7.4.4 Criteria to Pause Enrollment

Enrollment will be paused if any of the following criteria is met:

- 1) Any subject with grade 4+ RT-related adverse events
or
- 2) Subject incidence of the following Grade 4+ CAR-T-related adverse events lasting more than 7 days is > 33%:
 - Neurologic toxicities
 - CRS (per ASTCT 2019)
 - Other non-hematological serious adverse event
 - Infection (treatment-related)

DF/HCC Adverse Event Reporting Guidelines

Investigative sites within DF/HCC will report AEs directly to the DFCI Office for Human Research Studies (OHRS) per the DFCI IRB reporting policy.

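### Do the one-event enrolment pause in 7.4.4 and the one-event study stop in 12.3 conflict, or leave the safety trigger unworkable?

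*Combined protocol and SAP*

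**What the plan says.** Section 7.4.4 opens with "Enrollment will be paused if any of the following criteria is met" and lists first "Any subject with grade 4+ RT-related adverse events". It names no adjudicator and no review date. Section 7.4.1 supplies the relatedness call: "investigators must assess whether the adverse event is possibly related to 1) CAR T cell therapy product 2) RT", answered yes or no on the case report form. Under 7.4.2, serious events "must be submitted within 24 hours following the investigators knowledge of the event".

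Section 12.3 sets two numbered looks: "The SRT will review safety data when 3 and 10 subjects treated have had the opportunity to be followed for 30 days, respectively". The next sentence sets the study stop: "stopped if any patients develop grade 4 or higher toxicity attributed to RT rather than to lymphoma progression or other cause as per SRT". A further paragraph has the SRT review adverse events "on a regular basis throughout subject treatment in Phase 2 of the study" and adds: "The sponsor may request additional reviews by the SRT if safety concerns are identified".

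Section 11.2 describes the SRT as the study sponsor together with Kite/Gilead and gives it a recommending role. The DF/HCC monitoring committee reviews the protocol up to four times a year. The synopsis points to Sections 13.2 and 8.4.4 for monitoring.

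**The concern.** Grade 4 or higher toxicity in the RT field is what 12.2 names as the main worry, so this is the trial's central safety trigger. One event appears to call for two different actions, a pause in one place and a stop in another. Three things that staff would want are not written:

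- **Timing.** The stop sentence follows the looks at 3 and 10 subjects and does not say whether it acts only then. The regular-review sentence refers to a Phase 2, which this pilot does not have.
- **Authority.** The SRT recommends in 11.2, yet in 12.3 the study stops.
- **Restart.** Nobody is named who may lift a pause if the SRT does not attribute the event to RT.

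The synopsis pointers do not help: 8.4.4 does not exist in the current numbering, and 13.2 is now Subject Confidentiality.

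There is also an estimation worry. If the trial stops at its first event, the observed proportion is biased upward. The primary endpoint in 12.1 is a toxicity rate, and 12.2 says a larger study can be sized from the events seen.

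**Working it through.** **The two rules side by side**

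| | 7.4.4 | 12.3 |
|---|---|---|
| Trigger | one subject, grade 4+, RT-related | one patient, grade 4+, attributed to RT |
| Who judges | not named; investigator call in 7.4.1 | SRT |
| Excludes progression or other cause | not stated | yes |
| Action | pause enrolment | stop study |
| Tied to a scheduled look | no | not stated |

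The investigator's standard is possible relatedness, which is broader than SRT attribution after other causes are excluded. Pausing on the first and stopping on the second obeys both sections.

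**How often the trigger would fire.** The plan gives no operating characteristics for either rule and no event rate, so the true rate p is assumed. The planned number is 20 (12.2). Write q = 1 − p and treat patients as independent.

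- At least one event in 20: 1 − q^20.
- First event in patients 11 to 20: q^10 − q^20.
- Expected number treated if the stop acts at once: sum of q^k for k = 0 to 19.
- Expected number treated if it acts only at the two looks: 3 + 7q^3 + 10q^10.

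| p | At least one in 20 | First in 11–20 | Treated, at once | Treated, looks only |
|---|---|---|---|---|
| 1% | 18.2% | 8.6% | 18.2 | 18.8 |
| 2% | 33.2% | 14.9% | 16.6 | 17.8 |
| 5% | 64.2% | 24.0% | 12.8 | 15.0 |
| 10% | 87.8% | 22.7% | 8.8 | 11.6 |

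The last two columns differ by about 2.2 patients at 5% (15.0 − 12.8) and 2.8 at 10% (11.6 − 8.8). That difference assumes enrolment continues between an event and the next look. Section 7.4.4 prevents this, because the pause acts on the event itself. The third column is therefore the chance of an event after the last numbered look, not the chance that an event is missed.

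**Bias of the crude proportion.** Suppose the stop acts continuously, with m further patients already started when the first event occurs in patient k, and m_k = min(m, 20 − k). The mean of x/N is the sum over k = 1 to 20 of p q^(k−1) (1 + m_k p)/(k + m_k).

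| p | m = 0 | m = 1 | m = 3 |
|---|---|---|---|
| 1% | 3.4% | 2.5% | 1.9% |
| 2% | 6.6% | 4.9% | 3.6% |
| 5% | 14.7% | 10.8% | 8.1% |
| 10% | 25.2% | 18.6% | 14.4% |

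The values m = 1 and 3 assume 20 patients evenly spread over a year (365/20 ≈ 18 days apart) and events known 30 or 60 days after RT starts. At a true 5% the inflation is 2.9-, 2.2- or 1.6-fold.

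**Would a stopping-adjusted analysis help?** Take m = 0. With the first event in patient 12, the crude estimate is 1/12 = 8.3%, with ordinary exact 95% interval 0.2% to 38.5%. The median-unbiased estimate solves [1 − q^11] + 0.5 p q^11 = 0.5, giving 5.9%. Its adjusted interval runs from 1 − 0.975^(1/12) = 0.2% to 1 − 0.025^(1/11) = 28.5%. The lower limits agree, and the ordinary upper limit is the wider one. Averaged over trials at a true 5%, the median-unbiased estimate is 12.1% against 14.7% crude.

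Coverage of the ordinary exact interval under this stop:

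- p = 1%: it misses only if the first event is in patient 1 or 2 (lower limits 2.5% and 1.3%), with probability 0.0100 + 0.0099 = 0.0199. Coverage is 98.0%.
- p = 2%: it misses only if the first event is in patient 1, with probability 0.02. Coverage is 98.0%.
- p = 5% and 10%: no outcome misses. Coverage is 100%.
- p = 20%: it misses only with no event in 20 (upper limit 1 − 0.025^(1/20) = 16.8%), with probability 0.8^20 = 0.0115. Coverage is 98.8%.

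**The case for a change.** The strongest case for a change is that safety is the primary objective, so a central trigger should not depend on inference. Even if the stop is read as continuous and the Phase 2 wording as leftover template text, three things stay unwritten: a deadline for SRT attribution, the decision-maker, and the route back from a pause. At an assumed 5% rate the chance of stopping is 64.2% under a continuous reading and 40.1% (1 − 0.95^10) if only the two looks count. The remedy would cost a few sentences.

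Part of this stands: no section gives an attribution deadline or says who lifts a pause. The rest is weaker. Section 12.3 commits the SRT to regular review in mandatory terms, and its stop sentence covers any patient, so a discretionary sponsor request is not the only route to the SRT. The sponsor sits on the SRT, so recommending and stopping do not set two separate bodies against each other. A missing restart rule errs towards keeping enrolment closed.

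The bias is real if the stop acts continuously. It concerns one part of an all-grade descriptive endpoint. Section 12.2 itself limits claims to what a pilot can establish, and its reference to sizing a later study is permissive. The proposed estimator removes little of the bias.

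**Conclusion.** No change to the plan follows. The two rules are compatible as written. Following the text halts enrolment on the first grade 4 or higher RT-related event, whichever reading of 12.3 is taken. What is missing is procedural detail that the sponsor, SRT and investigators can settle when an event occurs; which action then applies is for them and the clinicians. The Phase 2 wording and the old section numbers are clerical: 8.4.4 is evidently the current 7.4.4, and 13.2 evidently meant the present 11.2. They can be tidied whenever the document is next revised.

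On estimation, the crude grade 4 or higher proportion could average 1.6 to 2.9 times a true 5% under continuous stopping. Section 12.4 promises exact intervals for response and only tabulated incidence for toxicity. An analyst who adds an exact interval and mentions the stopping rule gives a fair account, with 98% to 100% coverage. A stopping-adjusted estimator is a preference, with a modest gain (12.1% against 14.7%).

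This rests on assumed event rates, independent patients, no further patients started for the interval and coverage results, and the investigator's possible-relatedness call catching the events that the SRT would later attribute to RT.

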12.4 Analysis of Primary and Secondary Endpoints

Planned Method of Analysis

The primary analysis of all treated subjects will take place once they have had the opportunity to be followed for 6 months.

Descriptive analyses may occur at any time.

Objective Response Rate

The incidence of objective response and exact 2-sided 95% confidence intervals will be generated.

Duration of Response

The competing-risk analysis method ^{24,25} will be used to estimate the cumulative incidence of relapse. The cumulative incidence of relapse in the presence of non-disease related mortality (the competing risk) will be estimated along with 2-sided 95% confidence intervals at 3-month intervals.

Progression-free Survival

Kaplan-Meier estimates and 2-sided 95% confidence intervals will be generated for progression-free survival time. Estimates of the proportion of subjects alive and progression-free at 3-month intervals will be provided.

Overall Survival

Kaplan-Meier estimates and 2-sided 95% confidence intervals will be generated for OS. Estimates of the proportion of subjects alive at 3-month intervals will be provided.

Safety

Subject incidence rates of adverse events including all, serious, fatal, CTCAE version 5.0 Grade 3 or higher and treatment related AEs reported throughout the conduct of the study will be tabulated by preferred term and system organ class. Changes in laboratory values and vital signs will be summarized with descriptive statistics. The incidence of concomitant medications will be summarized.

Tables and/or narratives of deaths through the long-term follow-up and treatment related SAEs will be provided.

12.5 Reporting and Exclusions

The statistical reporting of the safety and efficacy endpoints will be compared to historical controls of patients with refractory disease following CAR T cell therapy who did not undergo RT. Subject incidence rates of axicel or tisacel-related adverse events, and ORRs will be summarized. DOR, PFS, and OS will also be summarized.

Analysis Subsets

Access to Individual Subject Treatment Assignments

This is a single arm, open-label study and subjects and investigators will be aware of treatment received. Data handling procedures for the the study will be devised to reduce potential sources of bias and maintain the validity and credibility of the study. These procedures will be outlined in the study statistical analysis plan and Trial Integrity Document.

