2.1 Study Design

Study 19-861 is a single center, pilot study evaluating the feasibility safety and efficacy of radiotherapy in patients with hematologic malignancies who will undergo any CD19-targeted CAR T cell therapy.

Approximately 20 subjects with hematologic malignancies with refractory disease following CAR-T cell therapy, including DLBCL, PMBCL, high grade lymphoma, TFL, or mantle cell lymphoma will be enrolled to evaluate the addition of radiotherapy in terms of achieving partial or complete response, and disease-free survival, as applicable. Specimens will be collected for translational analysis to study the interaction of RT and the immune microenvironment.

If addition of radiotherapy is safe and effective in these patients, RT may be a useful adjunct in patients with early refractory disease following CAR T cell therapy. A larger study would be done to investigate important determinants of eliciting RT response following CAR T cell therapy.

For study requirements assigned to each study period, please refer to the schedule of assessments (SOA) and [Section 11](#) for details.

Each subject will proceed through the following study periods:

- Screening
- Enrollment
- RT Treatment Period
- Post treatment assessment period with a biopsy (research) and PET/CT following RT (as standard of care)
- Long term follow-up period

A study schema is drawn out and described at the end of the protocol synopsis section.

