In addition, the international, multicohort retrospective non-Hodgkin lymphoma research (SCHOLAR-1) study retrospectively evaluated outcomes in patients with chemorefractory DLBCL, PMBCL, and TFL. SCHOLAR-1 integrated data from two Phase 3 studies (LYSARC-CORAL and Canadian Cancer Trials Group LY.12) and 2 observational cohorts (MD Anderson Cancer Center and Mayo Clinic/University of Iowa Specialized Program of Research Excellence). Among 861 patients, 635 were included based on chemorefractory search criteria. Outcomes were consistently poor, regardless of refractory subgroup and across cohorts. The results of SCHOLAR-1 indicated that patients with chemorefractory, aggressive DLBCL represent a homogenous patient population with a response rate of 26% (complete response [CR] rate of 7%) and median overall survival of 6.3 months¹⁹.

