3.2 Radiation Therapy for Refractory Lymphoma/Leukemia Following CAR T Cell Therapy

3.2.1 Background and Significance

MGH is on the forefront of academic institutions employing chimeric antigen receptor (CAR) T cell therapy, with 200+ patients already treated at MGH since the first FDA approval of axicabtagene ciloleucel; Yescarta¹ and tisacel (tisagenlecleucel; Kimrayah)² in 2017. Eligible patients for these commercial CAR T cell products have ALL (acute lymphoblastic leukemia) or relapsed or refractory large B cell lymphoma after at least 2 lines of systemic therapy¹. In addition, 30 new protocols of investigational CAR T cell therapy are underway at MGH, making it amongst the most active cellular therapy research programs across the world.

CAR T cell therapy is an exciting example of genetically modifying a patient's T cells to target tumor cells for death for patients with the above relapsed/refractory hematologic malignancies who otherwise have very limited, if any, remaining options to achieve cure. A patient first undergoes leukapheresis to collect peripheral blood mononuclear cells (PBMCs)¹. The T cells are isolated in a manufacturing laboratory and are genetically engineered most commonly via a viral vector to target an antigen displayed by the patient's tumor cells, which thus far has been CD19. These cells are then expanded and cryopreserved, for shipment back to the hospital. The patient is

admitted for infusion of the CAR T cells, basically a re-introduction of modified T cells into the patient's body. The time from eligibility determination for CAR T cells to the infusion of the CAR T cells can take as long as 2-3 months¹.

While response rates range from 50 - 80%, durable responses are only seen in 30-40% of patients at long term time points, demonstrating that 60% of patients will eventually relapse following CAR T cell therapy²⁻⁴. Although, the best predictor of durable response is the ability for a patient to achieve a complete response (CR), only 40-52% of patients will achieve CR at early day 30 restaging. Of the remaining patients with partial response, stable disease, or progressive disease, only 10-15% will subsequently convert to a CR at later timepoints without any clear predictor of later response emphasizing the need for better consolidative strategies.

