6.3 Excluded Medications

Corticosteroids and other immunosuppressive drugs should also be avoided for 3 months after CAR T cell administration, unless used to manage CAR T cell-related toxicities. Other medications that might interfere with the evaluation of the investigational product, such as non-steroidal anti-inflammatory agents should also be avoided for the same time period unless medically necessary. Physiologic steroids (less than or equal to 5mg/day) will be allowed on study.

Treatment for lymphoma such as chemotherapy, immunotherapy, targeted agents, radiation, and high dose corticosteroid, other than defined/allowed in this protocol, and other investigational agents are prohibited, except as needed for treatment of disease progression after the CAR T cell infusion and radiation therapy. Patients will be allowed to remain on maintenance therapy (ibrutinib, revlimid, etc) if these medications were initiated prior to and continued during CAR-T infusion.

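### Section 12.5 defines historical controls by absence of RT and not by their other therapy, so it compares RT-first with any non-RT management and cannot show the effect of adding RT

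*Combined protocol and SAP*

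**What the plan says.** The efficacy question is in Section 2.1: about 20 patients are enrolled "to evaluate the addition of radiotherapy in terms of achieving partial or complete response, and disease-free survival".

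Section 6.3 fixes the background treatment of trial patients. "Treatment for lymphoma such as chemotherapy, immunotherapy, targeted agents, radiation, and high dose corticosteroid, other than defined/allowed in this protocol", together with other investigational agents, "are prohibited, except as needed for treatment of disease progression after the CAR T cell infusion and radiation therapy". Maintenance drugs started before CAR T and continued during it may go on.

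Section 12.5 supplies the only planned comparison: safety and efficacy endpoints "will be compared to historical controls of patients with refractory disease following CAR T cell therapy who did not undergo RT". It gives no condition on the controls' other therapy, and no source or period for them. It refers to an SAP only for data-handling procedures to limit bias, not for the choice of controls.

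Section 12.1 classes as non-responders those with no objective response by data cutoff. It gives no rule for new anti-lymphoma therapy in ORR, DOR or PFS, and Section 12.4 adds none. It also calls the ORR analysis descriptive. Section 6.4 and Table 3 collect subsequent therapy for trial patients, but no endpoint definition uses it.

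**The concern.** To isolate the addition of RT, the control course should differ from the trial course in RT and in nothing else that matters. Here two things can differ at once. Trial patients have RT and, until progression, no new systemic therapy. Controls have no RT but may have started salvage at the refractory scan. Matching controls on the entry criteria would not cure this, because treatment begun after the refractory scan is not an entry criterion.

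The control ORR and PFS then depend on the share of controls who were salvaged, which has nothing to do with RT. A difference from the trial group, or the lack of one, would have no clear cause. Section 12.2 says the results will be used to design a larger study, so a misread comparison could carry forward. The plan already sees the issue for safety: Section 7.4.1 ends non-serious adverse event reporting when a new anticancer therapy starts. Efficacy has no counterpart.

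**Working it through.** **Step 1. Treatment rules side by side.**

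| | Trial patients | Historical controls |
|---|---|---|
| RT | Yes | None (12.5) |
| New systemic therapy before progression | Barred (6.3) | No condition |
| Maintenance from before CAR T | May continue (6.3) | No condition |
| New therapy after progression | Allowed (6.3), recorded (6.4, Table 3) | No condition; recording not mentioned |
| Response after new therapy | Not excluded, up to data cutoff (12.1) | No rule |

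The second row is the asymmetry. The last row shows that the trial ORR is not purely an RT response rate either.

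**Step 2. Does the plan put a figure on this comparison?** No. The one sample-size figure is the 19 in Section 12.2. It reproduces: n0 = 1.96² × 0.25 / 0.10² = 96.04, and with a population of 24, n = 96.04 / (1 + 95.04/24) = 19.36. Controls do not enter it, and no test, level or threshold is stated for the historical comparison.

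**Step 3. How far could the control mix move the benchmark?** The inputs are stand-ins from the plan:

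- b, the rate without salvage: 10-15%, midpoint 12.5%. Section 3.2.1 says of patients not in CR at day 30 that "only 10-15% will subsequently convert to a CR at later timepoints". This is CR only.
- r, the rate with salvage: ORR 14% (Section 3.1.1 and Table 1, refractory to second line) to 26% (Section 3.1.2, chemorefractory disease), with CR 7% in the latter. These are not post-CAR-T patients.

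With s the share of controls salvaged, control rate = (1 - s) × b + s × r. For b = 12.5% and r = 26%:

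| s | 0% | 25% | 50% | 75% | 100% |
|---|---|---|---|---|---|
| Control rate | 12.5% | 15.9% | 19.3% | 22.6% | 26.0% |

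The shift from s = 0 to s = 100% is r - b:

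- r = 26%: 26 - 12.5 = +13.5 points (+11 to +16 for b from 15% to 10%)
- r = 14%: 14 - 12.5 = +1.5 points (-1 to +4)
- r = 7%, CR only: 7 - 12.5 = -5.5 points (-8 to -3)

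With r = 26%, a 5-point shift needs s = 5 / (26 - b) = 31%, 37% or 45% for b = 10%, 12.5% or 15%.

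**Step 4. What that means at n = 20.** Take an invented result of 7/20 (35%, exact 95% CI 15.4% to 59.2%). The exact one-sided binomial tail is 0.008 against 12.5% and 0.247 against 26%. The same result reads differently according to a control mix that the plan leaves open. The one-sided tail is my device, not the plan's.

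**The case against.** The strongest reply is that this is a small pilot with safety primary, ORR secondary and descriptive, and no test attached to the controls. That stands and limits how much the point matters. A descriptive comparison still needs a comparator whose treatment is known.

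Several stronger readings are tempting, and the documents do not support them:

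- *The trial group is RT alone.* Section 6.3 allows continued maintenance, and therapy for progression after RT.
- *The controls are every refractory patient, a mix of untreated and salvaged.* Section 12.5 permits that mix by its silence. It does not say it.
- *The plan will decide from this comparison whether RT is a worthwhile adjunct.* Section 2.1 makes that remark conditional on RT being safe and effective, then proposes a larger study. It does not refer to the historical controls, and no decision rule does.
- *Salvaged controls raise the benchmark by 13.5 points.* That figure subtracts a CR rate from an ORR in a population not treated with CAR T. The 10-15% is drawn from a group that includes partial responders, so the ORR without salvage could exceed 12.5% and narrow the gap. On CR for both inputs, the sign reverses. Each shift is also smaller than the width of the interval for 7/20.

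It can also be said that asking about the addition of RT does not settle the estimand, and that RT-first versus non-RT management is a legitimate contrast. I accept that, provided it is labelled as such.

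A remedy that simply stops control follow-up at new therapy has its own faults. The clinical course may drive the start of salvage, so the stopping can be informative, and a patient salvaged at the refractory scan would be left unclassified. Nor would it align start dates: PFS runs from RT completion, which controls lack, and after RT the first scheduled PET-CT is at Month 6 from CAR T infusion. Those gaps are separate and remain.

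**Conclusion.** The point holds as a limit on interpretation. New systemic therapy is restricted in trial patients and unrestricted in the control definition, and no other section repairs this. The comparison in Section 12.5 is RT-first versus any non-RT management, and neither a difference nor its absence can be attributed to adding RT.

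Neither size nor direction can be established from the documents. The illustration runs from -5.5 to +13.5 points at the midpoint base rate (-8 to +16 over the 10-15% range). It assumes that the late CR conversion rate can stand for unsalvaged controls and that pre-CAR-T salvage rates can stand for salvaged ones. Neither assumption is secure. Because even the sign is uncertain, a reader could not correct for the control mix afterwards. The point is worth fixing before any control data are examined, and it leaves the primary safety endpoint untouched.

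**What to change.** Amend Section 12.5 or the SAP as follows.

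1. Record each control's first management after the refractory scan (observation or continued maintenance; new systemic therapy) and its date. Show ORR, PFS and OS by that grouping as well as overall. If only aggregate published controls are available, state their treatment mix and do not attribute differences to adding RT.
2. For trial patients, count as RT responses only those before the first new anti-lymphoma therapy, using the data from Section 6.4 and Table 3. Apply the same rule to observed controls. Controls who start salvage at the refractory scan go in the salvage group; they are neither dropped nor counted as non-responders.
3. Report PFS both with and without censoring at new therapy, and note that such censoring may be informative.
4. Label the overall comparison, OS included, as RT-first versus non-RT management.

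The cost is the wording and, if controls come from chart review, one more field with its date. Trial-side data are already collected, and no patient's treatment changes. The control subgroups will be smaller, with wider intervals, and they are defined by treatment choices related to prognosis, so the display is descriptive only.
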